### **Rationale for Amendment**

Editorial change, and revision to better fit the actual situation at investigational sites.

### **Page 94, Appendix C Schedule of Study Procedures (Part B – Weeks 49 to 96)**

#### **Existing Text**

Abbreviations: WK = Week; D = Day; ECOG = Eastern Cooperative Oncology Group; QOL = quality of life; SFU = safety follow-up

...

- b Additional examinations/assessments may be performed at the discretion of the investigator.

...

#### **Revised Text**

Abbreviations: WK = Week; D = Day; ECOG = Eastern Cooperative Oncology Group; QOL = quality of life; SFU = safety follow-up

...

- b Additional examinations/assessments may be performed at the discretion of the investigator **or sub-investigator**.

...

### **Rationale for Amendment**

Correction of typographical error (Note: Does not apply to English protocol.), and revision to better fit the actual situation at investigational sites.

### **Page 95, Appendix D Schedule of Blood Samples Collection for Pharmacokinetic Analysis (Part A)**

#### **Existing Text**

Abbreviations: WK = week; D = day

...

- c Blood samples for PK analysis will be collected within 1 hour before dosing.

...

#### **Revised Text**

Abbreviations: D = day

...

- c Blood samples for PK analysis will be collected within 1 hour before dosing.

...

### **Rationale for Amendment**

Editorial change.

**Page 96, Appendix E Schedule of Blood Samples Collection for Pharmacokinetic Analysis (Part B)**

**Existing Text**

Time Point a	Dosing Time Point b								
	WK1			WK2	WK 3	WK 5	WK 25	WK 37	WK 49
	D1 c	D2	D4	D1	D1	D1	D1	D1	D1
Before dosing d	X	X	X	X	X	X	X	X	X
2 hours postdose	X					X			

Abbreviations: WK = week; D = day

...

**Revised Text**

Time Point a	Dosing Time Point b								
	WK1			WK2	WK3	WK5	WK25	WK37	WK49
	D1 c	D2	D4	D1	D1	D1	D1	D1	D1
Before dosing d	X	X	X	X	X	X	X	X	X
2 hours postdose (± 20 min)	X					X			

Abbreviations: WK = week; D = day

...

5.3.2 Vital Signs, Physical Findings, and Other Observations Related to Safety	
5.4 Displays of Treatment-Emergent Adverse Events (Japanese)	
6 Safety Analysis (Part B)	53
6.1 Treatment-Emergent Adverse Events	53
6.1.1 Overview of Treatment-Emergent Adverse Events	53
6.1.2 Displays of Treatment-Emergent Adverse Events	54
6.2 Pretreatment Events	56
6.2.1 Displays of Pretreatment Events	56
6.3 Laboratory and Other Safety Data	57
6.3.1 Laboratory Test Results	57
6.3.2 Vital Signs, Physical Findings, and Other Observations Related to Safety	60
6.4 Displays of Treatment-Emergent Adverse Events (Japanese)	62
7 Significance Level and Confidence Coefficient (Part A and Part B)	62
Amendment History	63
Appendix 1. Amendments from the Previous Version	1
Appendix 2. Criteria for Markedly Abnormal Values and Elevated Liver Enzyme	1
Appendix 3. QOL Scoring Procedures	1

Glossary

- Treatment-emergent adverse event (TEAE): An adverse event whose date of onset occurs on or after the start of study drug
- Descriptive statistics: number of subjects, mean, standard deviation (SD), maximum (max), minimum (min), and quartiles
- CV: coefficient of variation
- Randomized set: All subjects who were randomized. The first maintenance dose prescribed will be used as the treatment group when conducting analyses.
- Treatment group: For part A, the assigned cohort will be the treatment group. For part B, the first maintenance dose prescribed will be the treatment group.
- PK: pharmacokinetic
- MAV: markedly abnormal value
- ATC: anatomical therapeutic chemical
- LDH: lactic dehydrogenase
- GGT: gamma-glutamyl transpeptidase
- CK (CPK): creatine phosphokinase/kinase
- Study Day: The day before the first dose of the study drug will be defined as Study Day -1 and the day of the first dose will be defined as Study Day 1. If the date of the observation is on the same date or after the day of the first dose, Study Day will be calculated relative to Study Day 1. Otherwise, Study Day will be calculated relative to Study Day -1.
- Follow-up Day: The day after the last dose of the study drug will be defined as Follow-up Day
 1. Follow-up Day will be calculated relative to Day 1.

Definition of Visit Window

When calculating Study Day relative to a reference date (i.e., date of first dose of study drug [Day 1]), if the date of the observation is on the same date or after the reference date, it will be calculated as: date of observation - reference date + 1; otherwise, it will be calculated as: date of observation - reference date. Hence, reference day is always Day 1 and there is no Day 0. When calculating Study Time relative to a reference time (i.e., time of each dose of study drug), it will be calculated as: time of observation - reference time.

When calculating Follow-up Day relative to a reference date (i.e., date of last dose of study drug [Follow-up Day 0]), it will be calculated as: date of observation - reference date. Hence, reference day is always Follow-up Day 0.

All evaluable data (i.e., non-missing and acceptable according to the Handling Rules for Analysis Data) will be handled according to the following rules.

For each visit, observation obtained in the corresponding time interval will be used. If more than one observation lies within the same visit window, the observation with the closest Study Day/Study Time to the scheduled Study Day/Study Time will be used. If there are two observations equidistant to the scheduled Study Day/Study Time, the later observation will be used. This does not apply to the end of study visit. For the end of study visit, the last observation obtained in the corresponding time interval will be used.

<Part A>

PSA

Visit	Scheduled Study Day (days)	Time Interval (days) Study Day
Baseline (Week 0)	Study Day: 1	-28 - 1
D28	Study Day: 28	2 - 35

Pharmacokinetic Assessments

		Time In	terval
Visit	Scheduled Study Time (hours)	Study Day (days)	Study Time (hours)
D1	-1	1	-3.00 - 0.00
D1	0.5	1	0.33 - 0.67
D1	1	1	0.75 - 1.24
D1	1.5	1	1.25 - 1.74
D1	2	1	1.75 - 2.33
D1	4	1	3.67 - 4.33
D1	6	1	5.50 - 6.50
D1	8	1	7.50 - 8.50
D1	12	1	11.00 - 13.00
D2	-1	2	-2.00 - 0.00
D3	-1	3	-2.00 - 0.00
D3	2	3	1.67 - 2.33
D7	-1	7	-2.00 - 0.00
D7	2	7	1.67 - 2.33
D12	-1	12	-2.00 - 0.00
D13	-1	13	-2.00 - 0.00
D14	-1	14	-2.00 - 0.00
D14	0.5	14	0.33 - 0.67

		Time In	terval	
Visit	Scheduled Study Time (hours)	Visit Scheduled Study Time (hours) (days)		Study Time (hours)
D14	1	14	0.75 - 1.24	
D14	1.5	14	1.25 - 1.74	
D14	2	14	1.75 - 2.33	
D14	4	14	3.67 - 4.33	
D14	6	14	5.50 - 6.50	
D14	8	14	7.50 - 8.50	
D14	12	14	11.00 - 13.00	
D15	Study Day: 15	15	16.00 - 34.00 (from last dose)	
D21	Study Day: 21	18 - 24	16.00 - 34.00 (from last dose)	
D28	-1	28	-2.00 - 0.00	
D28	1	28	0.75 - 1.24	
D28	2	28	1.67 - 2.33	
D28	4	28	3.67 - 4.33	
D28	8	28	7.50 - 8.50	
D28	12	28	11.00 - 13.00	
D29	24 (from D28)	29	23.00 - 25.00 (from D28)	
D30	48 (from D28)	30	44.00 - 52.00 (from D28)	
D31	72 (from D28)	31	68.00 - 76.00 (from D28)	
D35	168 (from D28)	35	164.00 - 172.00 (from D28)	

Visit	Scheduled Study Day (days)	Time Interval (days) Study Day
Baseline (Week 0)	Study Day: 1	-28 - 1
D2	Study Day: 2	2
D3	Study Day: 3	3 - 4
D7	Study Day: 7	5 - 10
D14	Study Day: 14	11 - 17
D21	Study Day: 21	18 - 24
D28	Study Day: 28	25 - 29
D31	Study Day: 31	30 - 34
D35	Study Day: 35	35

Pharmacodynamic Assessments

Laboratory Tests (Hematology, Biochemistry, Urinalysis)

	Scheduled Study Day	Time Interval (days)	
Visit	(days)	Study Day	Follow-up Day
Baseline (Week 0)	Study Day: 1	- 1	
D7	Study Day: 7	2 - 10	< 15
D14	Study Day: 14	11 - 17	< 15
D21	Study Day: 21	18 - 24	< 15
D28	Study Day: 28	25 - 42	< 15
SFU	Follow-up Day: 40		15 - 40

Laboratory Tests (Lipid and Glycated Hemoglobin in Blood)

	Scheduled Study Day	Time Inter	val (days)
Visit	(days)	Study Day	Follow-up Day
Baseline (Week 0)	Study Day: 1	- 1	
D28	Study Day: 28	2 - 42	< 15

	Scheduled Study Day Time Interv		val (days)
Visit	(days)	Study Day	Follow-up Day
SFU	Follow-up Day: 40		15 - 40

Vital Signs, Weight

.	Scheduled Study Day	Time Interval (days)	
Visit	(days)	Study Day	Follow-up Day
Baseline (Week 0)	Study Day: 1	-28 - 1	
D7	Study Day: 7	2 - 10	< 15
D14	Study Day: 14	11 - 17	< 15
D21	Study Day: 21	18 - 24	< 15
D28	Study Day: 28	25 - 42	< 15
SFU	Follow-up Day: 40		15 - 40

12-Lead Electrocardiogram

	Scheduled Study Day	Time Inter	val (days)
Visit	(days)	Study Day	Follow-up Day
Baseline (Week 0)	Study Day: 1	-28 - 1	
D14	Study Day: 14	2 - 20	< 15
D28	Study Day: 28	21 - 42	< 15
SFU	Follow-up Day: 40		15 - 40

ECOG Performance Status

Visit	Scheduled Study Day (days)	Time Interval (days)	
		Study Day	Follow-up Day
Baseline (Week 0)	Study Day: 1	-28 - 1	

PSA			
Visit	Scheduled Study Day	Time Interval (days)	
VISIC	(days)	Study Day	
Baseline (Week 0)	Study Day: 1	-28 - 1	
WK5D1	Study Day: 29	2 - 42	
WK9D1	Study Day: 57	43 - 70	
WK13D1	Study Day: 85	71 - 98	
WK17D1	Study Day: 113	99 - 126	
WK21D1	Study Day: 141	127 - 154	
WK25D1	Study Day: 169	155 - 210	
WK37D1	Study Day: 253	211 - 294	
WK49D1	Study Day: 337	295 - 378	
WK61D1	Study Day: 421	379 - 462	
WK73D1	Study Day: 505	463 - 546	
WK85D1	Study Day: 589	547 - 630	
WK97D1	Study Day: 673	631 - 680	
WK13D1 (LOCF)	Study Day: 85	2 - 98	
End of Study		2 -	

<Part B>

Pharmacokinetic Assessments

	Time Interval		nterval
Visit	Scheduled Study Time (hours)	Study Day (days)	Study Time (hours)
WK1D1	-1	1	-3.00 - 0.00
WK1D1	2	1	1.75 - 2.33
WK1D2	-1	2	-2.00 - 0.00
WK1D4	Study Day: 4	3 - 6	16.00 - 34.00 (from last dose)

		Time Interval	
Visit	ScheduledStudy Time (hours)(days)		Study Time (hours)
WK2D1	Study Day: 8	7 - 12	16.00 - 34.00 (from last dose)
WK3D1	Study Day: 15	13 - 22	16.00 - 34.00 (from last dose)
WK5D1	Study Day: 29	23 - 43	-2.00 - 0.00
WK5D1	2	23 - 43	1.67 - 2.33
WK9D1	Study Day: 57	44 - 71	16.00 - 34.00 (from last dose)
WK13D1	Study Day: 85	72 - 99	16.00 - 34.00 (from last dose)
WK17D1	Study Day: 113	100 – 127	16.00 - 34.00 (from last dose)
WK21D1	Study Day: 141	128 - 155	16.00 - 34.00 (from last dose)
WK25D1	Study Day: 169	156 - 183	16.00 - 34.00 (from last dose)
WK37D1	Study Day: 253	233 - 274	16.00 - 34.00 (from last dose)
WK49D1	Study Day: 337	317 - 358	16.00 - 34.00 (from last dose)

Imaging Assessments

Visit	Scheduled Study Day (days)	Time Interval (days) Study Day
WK49D1	Study Day: 337	2 - 344
WK97D1	Study Day: 673	345 - 680

	Scheduled Study Day	Time Interval (days)	
Visit	(days)	Study Day	Follow-up Day
Baseline (Week 0)	Study Day: 1	-28 - 1	
WK5D1	Study Day: 29	2 - 42	< 15
WK9D1	Study Day: 57	43 - 70	< 15
WK13D1	Study Day: 85	71 - 112	< 15
WK21D1	Study Day: 141	113 - 154	< 15
WK25D1	Study Day: 169	155 - 238	< 15
WK45D1	Study Day: 309	239 - 322	< 15
WK49D1	Study Day: 337	323 - 378	< 15
WK61D1	Study Day: 421	379 - 462	< 15
WK73D1	Study Day: 505	463 - 546	< 15
WK85D1	Study Day: 589	547 - 630	< 15
WK97D1	Study Day: 673	631 - 687	< 15
SFU	Follow-up Day: 40		15 - 40

QOL Assessment

Pharmacodynamic Assessments (Excluding High-Sensitivity Serum Testosterone)

Visit	Scheduled Study Day (days)	Time Interval (days) Study Day
Baseline (Week 0)	Study Day: 1	-28 - 1
WK1D2	Study Day: 2	2 - 3
WK1D4	Study Day: 4	4 - 5
WK2D1	Study Day: 8	6 - 11
WK3D1	Study Day: 15	12 - 21
WK5D1	Study Day: 29	22 - 42
WK9D1	Study Day: 57	43 - 70
WK13D1	Study Day: 85	71 - 98

Visit	Scheduled Study Day (days)	Time Interval (days) Study Day
WK17D1	Study Day: 113	99 - 126
WK21D1	Study Day: 141	127 - 154
WK25D1	Study Day: 169	155 - 210
WK37D1	Study Day: 253	211 - 294
WK49D1	Study Day: 337	295 - 378
WK61D1	Study Day: 421	379 - 462
WK73D1	Study Day: 505	463 - 546
WK85D1	Study Day: 589	547 - 630
WK97D1	Study Day: 673	631 - 680

ECOG Performance Status

	Scheduled Study Day	Time Interval (days)	
Visit	(days)	Study Day	Follow-up Day
Baseline (Week 0)	Study Day: 1	-28 - 1	

Pharmacodynamic Assessments (High-Sensitivity Serum Testosterone)

Visit	Scheduled Study Day (days)	Time Interval (days) Study Day
Baseline (Week 0)	Study Day: 1	-28 - 1
WK2D1	Study Day: 8	2 - 11
WK3D1	Study Day: 15	12 - 21
WK5D1	Study Day: 29	22 - 42
WK9D1	Study Day: 57	43 - 70
WK13D1	Study Day: 85	71 - 98
WK17D1	Study Day: 113	99 - 126
WK21D1	Study Day: 141	127 - 154

Visit	Scheduled Study Day (days)	Time Interval (days) Study Day
WK25D1	Study Day: 169	155 - 210
WK37D1	Study Day: 253	211 - 294
WK49D1	Study Day: 337	295 - 344

N 71 - 4	Scheduled Study Day	Time Interval (days)	
Visit	(days)	Study Day	Follow-up Day
Baseline (Week 0)	Study Day: 1	- 1	
WK5D1	Study Day: 29	2 - 42	< 15
WK9D1	Study Day: 57	43 - 70	< 15
WK13D1	Study Day: 85	71 - 126	< 15
WK25D1	Study Day: 169	127 - 210	< 15
WK37D1	Study Day: 253	211 - 294	< 15
WK49D1	Study Day: 337	295 - 378	< 15
WK61D1	Study Day: 421	379 - 462	< 15
WK73D1	Study Day: 505	463 - 546	< 15
WK85D1	Study Day: 589	547 - 630	< 15
WK97D1	Study Day: 673	631 - 687	< 15
SFU	Follow-up Day: 40		15 - 40

Laboratory Tests (Hematology)

Laboratory Tests (Biochemistry)

Laboratory Tests (Biochemistry)			
	Scheduled Study Day	Time Interval (days)	
Visit	(days)	Study Day	Follow-up Day
Baseline (Week 0)	Study Day: 1	- 1	
WK5D1	Study Day: 29	2 - 42	< 15
WK9D1	Study Day: 57	43 - 70	< 15
WK13D1	Study Day: 85	71 - 98	< 15
WK17D1	Study Day: 113	99 - 126	< 15
WK21D1	Study Day: 141	127 - 154	< 15
WK25D1	Study Day: 169	155 - 182	< 15
WK29D1	Study Day: 197	183 - 210	< 15
WK33D1	Study Day: 225	211 - 238	< 15

	Scheduled Study Day	Time Interval (days)	
Visit	(days)	Study Day	Follow-up Day
WK37D1	Study Day: 253	239 - 266	< 15
WK41D1	Study Day: 281	267 - 294	< 15
WK45D1	Study Day: 309	295 - 322	< 15
WK49D1	Study Day: 337	323 - 378	< 15
WK61D1	Study Day: 421	379 - 462	< 15
WK73D1	Study Day: 505	463 - 546	< 15
WK85D1	Study Day: 589	547 - 630	< 15
WK97D1	Study Day: 673	631 - 687	< 15
SFU	Follow-up Day: 40		15 - 40

Laboratory Tests (Lipid and Glycated Hemoglobin in Blood, Urinalysis)

Scheduled Study Day		Time Interval (days)	
Visit	(days)	Study Day	Follow-up Day
Baseline (Week 0)	Study Day: 1	- 1	
WK5D1	Study Day: 29	2 - 42	< 15
WK9D1	Study Day: 57	43 - 70	< 15
WK13D1	Study Day: 85	71 - 126	< 15
WK25D1	Study Day: 169	127 - 252	< 15
WK49D1	Study Day: 337	253 - 378	< 15
WK61D1	Study Day: 421	379 - 462	< 15
WK73D1	Study Day: 505	463 - 546	< 15
WK85D1	Study Day: 589	547 - 630	< 15
WK97D1	Study Day: 673	631 - 687	< 15
SFU	Follow-up Day: 40		15 - 40

	Scheduled Study Day	Time Interval (days)	
Visit	(days)	Study Day	Follow-up Day
Baseline (Week 0)	Study Day: 1	-28 - 1	
WK3D1	Study Day: 15	2 - 21	< 15
WK5D1	Study Day: 29	22 - 98	< 15
WK25D1	Study Day: 169	99 – 252	< 15
WK49D1	Study Day: 337	253 - 420	< 15
WK73D1	Study Day: 505	421 - 588	< 15
WK97D1	Study Day: 673	589 - 687	< 15
SFU	Follow-up Day: 40		15 - 40

12-Lead Electrocardiogram

Vital Signs, Weight

	Scheduled Study Day	Time Interval (days)	
Visit	Visit (days)		Follow-up Day
Baseline (Week 0)	Study Day: 1	-28 - 1	
WK2D1	Study Day: 8	2 - 11	< 15
WK3D1	Study Day: 15	12 - 21	< 15
WK5D1	Study Day: 29	22 - 42	< 15
WK9D1	Study Day: 57	43 - 70	< 15
WK13D1	Study Day: 85	71 - 126	< 15
WK25D1	Study Day: 169	127 - 252	< 15
WK49D1	Study Day: 337	253 - 378	< 15
WK61D1	Study Day: 421	379 - 462	< 15
WK73D1	Study Day: 505	463 - 546	< 15
WK85D1	Study Day: 589	547 - 630	< 15
WK97D1	Study Day: 673	631 - 687	< 15
SFU	Follow-up Day: 40		15 - 40

Visit	Scheduled Study Day (days)	Time Interval (days) Study Day
Baseline (Week 0)	Study Day: 1	-28 - 1
WK25D1	Study Day: 169	2 - 252
WK49D1	Study Day: 337	253 - 420
WK73D1	Study Day: 505	421 - 588
WK97D1	Study Day: 673	589 - 713

Bone Mineral Density (DXA)

Others

- Duration of exposure to study drug (days) : date of last dose of study drug date of first dose of study drug + 1
- Dose intensity (mg/day): total amount of doses taken / duration of exposure to study drug (rounded to 1 decimal place)
- Relative dose intensity (%): (total amount of doses taken / total dose expected per initial dose) * 100 (rounded to 1 decimal place)
- Dosing compliance: (total amount of doses taken / total dose expected) * 100 (rounded to 1 decimal place)
- Disease duration (days): date subject signed Informed Consent Form date of diagnosis + 1
 - For the date subject signed Informed Consent Form, the year, the month, and the day will be used for the calculation.
 - If the year is unknown, then the date of diagnosis will be treated as missing. If the month is unknown, then the month will be treated as January and the day will be treated as the 1st day of the month. If only the day is unknown, then the day will be treated as the 1st day of the month for the calculation.
- PK parameters:
 - AUC_{last} --Area under the concentration-time curve from time 0 to time of the last quantifiable concentration.
 - AUC_{last, ss} --Area under the concentration-time curve from time 0 to time of the last quantifiable concentration, at steady state.
 - > AUC_{τ} --Area under the concentration-time curve during a dosing interval (= 24 hours).
 - > AUC_{τ , ss} --Area under the concentration-time curve during a dosing interval (= 24 hours), at steady state.
 - > AUC_{τ , ss}/D --Dose-normalized AUC_{τ}, at steady state.
 - CL/F_{ss} --Apparent clearance after extravascular administration, at steady state, calculated using AUC_τ.
 - ► C_{max} --Maximum observed concentration.
 - ➢ C_{max, ss} --Maximum observed concentration, at steady state.
 - \sim C_{max, ss}/D --Dose-normalized C_{max}, at steady state.
 - ► C_{min, ss} --Minimum observed concentration during a dosing interval, at steady state.
 - > λ_z --Terminal disposition phase rate constant.
 - > t_{max} --Time of first occurrence of C_{max} .
 - > $t_{max, ss}$ --Time of first occurrence of C_{max} , at steady state.
 - \blacktriangleright t_{1/2z} --Terminal disposition phase half-life.
 - V_z/F_{ss} --Apparent volume of distribution during the terminal disposition phase after extravascular administration, calculated using AUC_τ.

1 Study Subjects, Demographics, and Other Baseline Characteristics (Part A)

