## 6.0 STUDY DESIGN AND DESCRIPTION

### 6.1 Study Design

This is a multicenter phase 1, open-label, dose range-finding study to evaluate the tolerability, safety, PK, and pharmacodynamics of TAK-385 alone in hormone treatment-naive Japanese patients with non-metastatic prostate cancer.

This study consists of two parts: Part A, a dose-rising phase, and Part B, an expansion phase. The designs of Part A and Part B are shown in “Study Design and Treatment Schema” (Figure 6.a and Figure 6.b).

In Part A, three to six patients will be enrolled in each cohort. Whether or not the study will proceed to the next cohort or Part B will be determined through assessment of tolerability at the dose in question, based on the incidence of DLT in the evaluation period (treatment initiation to Day 28).

TAK-385 will be taken once a day for 28 days at the doses assigned to each cohort. Cohort 1 will receive a loading dose of 320 mg and a maintenance dose of 80 mg, Cohort 2 will receive a loading dose of 320 mg and a maintenance dose of 120 mg, Cohort 3 will receive a loading dose of 320 mg and a maintenance dose of 160 mg, and Cohort 4 will receive a loading dose of 360 mg and a maintenance dose of 120 mg. The doses will be taken orally at least 30 minutes before breakfast. Patients being switched to a GnRH agonist (eg, leuprorelin) or a GnRH antagonist (eg, degarelix) following the completion of TAK-385 treatment in Part A will first pass through a 1-week observation (no-treatment) period. However, patients whose treatments were discontinued because they met the discontinuation criteria (Section 7.5) during the 28-day treatment period will not have to pass through this observation period.

If tolerability is confirmed in Cohort 2, then the study will proceed to Cohort 3 and Part B simultaneously. The tolerability in Japanese of the maximum dose at which tolerability was found in 28-day multiple dosing in the overseas phase 1 single-/multiple-dose study (TAK-385\_C27001) (160 mg) will be evaluated for the purpose of checking the tolerability of dose escalation to 160 mg in Part B as well as the PK. In the overseas phase 1 single-/multiple-dose study (TAK-385\_C27001), no findings indicative of safety problems were obtained in multiple dosing for 28 days with 160 mg. However, if tolerability is not confirmed in Cohort 2, then a cohort will be added that will receive a loading dose of TAK-385 320 mg and a maintenance dose of 40 mg.

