**Table 6.b Study Schedule (Part B)**

Screening	Treatment Period	Continuation Treatment Period	Safety Follow-up
Outpatient			
Days -28 to -1 *1	Week 1, Day 1 *1 to Week 48, Day 7 *2	Week 49, Day 1 to Week 96, Day 7 *2	30 to 40 days after the last dose of TAK-385
Screening tests Assessment of eligibility, randomization	Tests, observations Treatment initiation Treatment completion	Tests, observations Treatment initiation Treatment completion	Initiation of other treatment Tests, observations

\*1: Day -1 and Day 1 are the day before treatment initiation and the day of treatment initiation, respectively.

\*2: Other treatments may be initiated starting on the day after the day of the last dose of TAK-385 (Week 48, Day 8 or Week 96, Day 8).

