### **9.3.8 Safety Follow-up**

The following tests, observations, and assessments will be performed as safety follow-up 30 to 40 days after the day of the last dose of study drug, and will be the final observations performed.

These same tests, observations, and assessments will be performed 30 to 40 days after the last dose of study drug for subjects who withdraw from the study as well.

The status of study completion will be entered into the eCRF for all subjects who receive study drug in Part A, and for all subjects who are randomized in Part B.

- Physical examination
- Vital signs
- Weight
- ECOG performance status
- 12-lead ECG
- Clinical laboratory tests (hematology, chemistry, metabolic panel, and urinalysis)
- Concomitant medications
- Concomitant therapies
- AEs

The following tests will be performed only in Part B.

- QOL assessments

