## 10.2 Procedures

### 10.2.1 Collection and Reporting of Adverse Events

#### 10.2.1.1 Collection Period of Pretreatment Events and Adverse Events

Pretreatment events will be recorded continuously from when informed consent is obtained until the first dose of study drug (Day 1). If it is decided that a subject should be withdrawn before the first dose of study drug, PTEs will be recorded until that point in time.

AEs will be recorded continuously from the start of study drug administration to subjects (Day 1) until the safety follow-up.

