#### 1) Adverse events

The following analysis will be performed for the safety analysis set.

A treatment-emergent adverse event (TEAE) refers to an event that occurs after the start of study drug administration.

The following TEAE will be tabulated by Part and by dose. TEAEs will be coded according to MedDRA and summarized by System Organ Class (SOC) and Preferred Term (PT).

- Frequency tabulations of all TEAEs
- Frequency tabulations of treatment-related TEAEs
- Frequency tabulations of all TEAEs by severity
- Frequency tabulations of treatment-related TEAEs by severity
- Frequency tabulations of TEAEs for which the study drug action taken was "treatment discontinuation"
- Frequency tabulations of serious TEAEs
- Frequency tabulations of all TEAEs by time of onset

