Appendix 2. Criteria for Markedly Abnormal Values and Elevated Liver Enzyme

(1) Criteria for Markedly Abnormal Values

1) Vital Signs, and 12-lead ECG (except Upper MAV Criteria of QTcF Interval)

For each parameter, all evaluable data (i.e., non-missing and acceptable according to the Handling Rules for Analysis Data) obtained after baseline will be classified as a MAV or not. The criteria in the table below will be used. The lower limit of the normal range and the upper limit of the normal range are abbreviated as LLN and ULN.

Vital Signs

			MAV Criteria	
Parameter	Gender	ender Age	Lower Criteria	Upper Criteria
Systolic Blood Pressure (mmHg)	-	-	<85	>180
Diastolic Blood Pressure (mmHg)	-	-	<50	>110
Pulse (bpm)	-	-	<50	>120
Body Temperature (°C)	-	-	<35.6	>37.7

12-lead ECG

D			MAV Criteria	
Parameter	Gender Age	Lower Criteria	Upper Criteria	
Heart Rate (bpm)	-	-	<50	>120
QT Interval (msec)	-	-	<=50	>=460
QTcF Interval (msec)	-	-	<=50	_

Classifying Subjects for the Overall Treatment Period

For each parameter and subject, classifications will be made according to the conditions i) to iii) provided below. The lower and the upper criteria will be considered separately.

- i) A subject with at least one evaluable data after baseline that meets the MAV criteria will be classified as a subject with MAV.
- ii) A subject who does not meet condition i) and has at least one evaluable data after baseline that doesn't meet the MAV criteria will be considered as a subject without MAV.
- iii) A subject who does not meet conditions i) or ii) will be excluded from the analysis of MAV for that parameter.

2) 12-lead ECG (Upper MAV Criteria of QTcF Interval)

All evaluable data (i.e., non-missing and acceptable according to the Handling Rules for Analysis Data) obtained after baseline will be classified as a MAV or not. The criteria in the table below will be used. Note that the observed value and the change from baseline used for classification should be measurements taken on the same day.

		ender Age	MAV Criteria		
Parameter	Gender		Lower Criteria	Upper Criteria	
QTcF Interval (msec)	-	-	-	If either of the following conditions is met: - observed value >=500 - change from baseline >= 30 and observed value >=450	

Classifying Subjects for the Overall Treatment Period

For each subject, classifications will be made according to the conditions i) to iii) provided below.

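### The SAP does not flag the start of the next GnRH drug, so events and values first arising after a switch can be counted in the by-dose TAK-385 safety tables

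*SAP*

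**What the plan says.** **TEAE definition.** The SAP glossary gives "An adverse event whose date of onset occurs on or after the start of study drug". Protocol section 13.1.7 says that a TEAE "refers to an event that occurs after the start of study drug administration". Both have a start and no end.

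**Collection.** Protocol 10.2.1.1: "AEs will be recorded continuously from the start of study drug administration to subjects (Day 1) until the safety follow-up". Protocol 9.3.8 places that visit "30 to 40 days after the day of the last dose of study drug, and will be the final observations performed". Laboratory tests, vital signs and a 12-lead ECG are repeated there.

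**Next drug.** For Part B, a note to protocol Table 6.b says: "Other treatments may be initiated starting on the day after the day of the last dose of TAK-385". In Part A, completers who switch to a GnRH agonist or antagonist "will first pass through a 1-week observation (no-treatment) period", while subjects who met discontinuation criteria "will not have to pass through this observation period" (protocol 6.1). The ban on these drugs in protocol 7.3.1 covers the treatment period and, in Part A, the observation week.

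**Worst-value tables.** The laboratory grade tables (SAP 5.3.1 and 6.3.1) and the liver-enzyme criteria (SAP Appendix 2) use all evaluable post-baseline data. The MAV rule in Appendix 2 reads "A subject with at least one evaluable data after baseline that meets the MAV criteria will be classified as a subject with MAV", under a heading that speaks of the overall treatment period.

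**Visit windows.** The SAP windows for laboratory tests, vital signs and ECG separate Follow-up Day below 15 from a safety follow-up visit at Follow-up Days 15 to 40.

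**The concern.** The safety tables are presented by TAK-385 dose, and they are the primary endpoint in both parts. A subject who moves to another GnRH drug is still observed for several weeks, and nothing in the SAP marks the point of the switch. An event that first appears on the next drug has the same status in the all-causality TEAE tables as one that appeared on TAK-385. A first QTcF or liver value beyond the limit at safety follow-up classes the subject as abnormal in the TAK-385 group.

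The protocol itself shows how this could occur. Section 4.1 says that GnRH agonists can cause a flare with temporary worsening of symptoms, which TAK-385 is not expected to cause, and section 10.1.3 treats worsening symptoms of progression as adverse events. Section 4.1.2.5 describes the QTc changes on TAK-385 as similar to those seen with castration by other compounds. At stake is whether a reader of a by-dose table can tell which drug a subject was taking when an event or value arose.

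**Working it through.** **1. The plan's own figure.** Protocol 13.3 gives 15 subjects per group an approximately 80% chance of showing an adverse event of true incidence 10%. 1 − 0.9^15 = 0.794, so it reproduces per group. It does not use follow-up time, and nothing below changes it.

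**2. What limits each output.**

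| Output | End stated in SAP | Practical end | Separated at the switch? |
|---|---|---|---|
| All-causality TEAE tables | none | safety follow-up | no |
| Maximum laboratory grade | none | safety follow-up | no |
| Elevated liver enzymes | none | safety follow-up | no |
| MAV | none in the rule; heading refers to treatment period | safety follow-up | no |
| By-visit laboratory, vital signs, ECG | visit window | safety follow-up shown as its own visit | by time, not by switch |

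**3. Share of observed days on which another GnRH drug is possible.** This takes the earliest permitted switch, so the figures are upper limits. Share = (follow-up days − drug-free days) / (treatment days + follow-up days).

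- Part B, 48 weeks (336 days): 30/366 = 8.2%; 40/376 = 10.6%.
- Part B, 96 weeks (672 days): 30/702 = 4.3%; 40/712 = 5.6%.
- Part A completer (28 days, 7 drug-free): 23/58 = 39.7%; 33/68 = 48.5%.

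**4. Effect on a table cell.** In a Part B group one subject is 1/15 = 6.7 percentage points. The documents give neither a switch rate nor an event rate on the next drug. As an illustration only, assume that all 15 subjects switch and that each has probability q of a given event arising from the next drug before safety follow-up. The chance that at least one such event enters the table is 1 − (1 − q)^15:

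- q = 1%: 14% (0.15 subjects expected)
- q = 5%: 54% (0.75 expected)
- q = 10%: 79% (1.5 expected)
- q = 20%: 96% (3.0 expected)

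If the event also has 10% incidence on TAK-385, independently, the tabulated incidence is 1 − 0.9 × (1 − q): 14.5%, 19% and 28% at q = 5%, 10% and 20%.

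**5. Remaining TAK-385 effect.** Protocol 4.1.2.5 gives a multiple-dose half-life of about 36 to 65 hours. Five half-lives are 5 × 36/24 = 7.5 days to 5 × 65/24 = 13.5 days, so an event in the first one to two weeks of follow-up could belong to either drug.

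**6. Time-of-onset table.** In SAP 6.1.2 the denominator for an interval is subjects with exposure or a TEAE during or after it. A 48-week completer has a last dose on Day 336 and follow-up to Day 366 to 376. That subject enters the Day 361 to 450 interval only by having an event, so this table does not isolate post-switch events cleanly.

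**The case against.** The case against rests on several points, most of which stand and narrow the concern.

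- **The data are not open-ended.** Collection stops at safety follow-up. This stands: the gap is a missing marker inside a bounded window.
- **All-causality tables do not attribute.** Drug-related TEAE tables are planned, and events reasonably explained by a concomitant medication can be rated not related (protocol 10.1.7). This stands in part. The same section lets an event be rated related when another medication may also be responsible, and the grade, liver and MAV tables have no causality filter.
- **A switch need not change a table.** Each subject counts once per preferred term or once at maximum intensity. Only a new term, a higher grade or a first qualifying value matters, and effects shared by the two drugs may already have been counted during 48 weeks on TAK-385. This stands. It does not cover effects that TAK-385 lacks, such as flare.
- **Few assessments are affected.** At Week 49 a Part B completer switches after that visit's assessments (protocol Appendix B), so only the safety follow-up visit is normally scheduled after a switch. This stands for the laboratory, vital-sign and ECG tables, but not for adverse events.
- **Part A is partly protected.** Completers have a drug-free week, and the DLT period closes at Day 28, so their DLT assessment is untouched. This stands.
- **Other rules may exclude values.** Evaluability depends on the Handling Rules for Analysis Data, which are not in the documents. Exclusion of some post-switch laboratory, vital-sign or ECG values cannot be ruled out. The TEAE definition carries no such qualifier.
- **A fixed cut would do harm.** Limiting the worst-value tables to Follow-up Day below 15 would drop late abnormalities, including liver values, in subjects who never switched. Removing events from the main tables would also depart from the all-TEAE tabulations in protocol 13.1.7. Both stand and shape the fix.

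**Conclusion.** The concern holds in limited form. Another GnRH drug can start before safety follow-up: from the day after the last dose in Part B, after one week in Part A completers, and at once in Part A discontinuers. The SAP has no cut or flag at that start, so events and values first arising on the next drug can be counted in the by-dose all-causality TEAE, maximum-grade, liver-enzyme and MAV tables.

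In Part B the share of observed days is at most 8% to 11% at 48 weeks and 4% to 6% at 96 weeks, assuming an immediate switch. One affected subject moves a group's incidence by 6.7 points. The probabilities in the working rest on an assumed q and on every subject switching.

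A reader might go further and infer that the next drug's effects are necessarily credited to TAK-385, that every switch contaminates the primary endpoint, or that incidence is biased by 8% to 11%. The documents do not support this. Counting in an all-causality table is not attribution, a switch alters a cell only under the conditions above, a person-time share is not an incidence bias, and part of the follow-up can still reflect TAK-385. The analyses are descriptive, and no sample-size figure changes. This is a worthwhile, low-cost improvement rather than a fault that undermines the trial.

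**What to change.** In the SAP:

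1. Derive the start date of the first subsequent prostate-cancer therapy from the concomitant-medication record, which protocol 9.1.16 carries through safety follow-up. Flag TEAEs with onset, and laboratory, vital-sign and ECG values dated, on or after it.
2. Keep the protocol's all-TEAE tables as they are. Add by-dose TEAE, maximum-grade, liver-enzyme and MAV summaries that exclude flagged data, with the flagged data in a separate column.
3. Do not apply a blanket Follow-up Day limit to subjects who have not switched.
4. Make the heading of the MAV classification in Appendix 2 agree with its rule, which uses any evaluable value after baseline.
5. State whether the Handling Rules for Analysis Data already exclude any post-switch values.

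The cost is one derived flag and extra columns. The downside is that a late TAK-385 effect arising after a switch appears in the separate column and the full tables, but not in the pre-switch summary. No data are lost, and trial conduct does not change.
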